## 12. PRIOR ANTI-CANCER THERAPY

Prior oncology therapy will be summarized for the FAS. Prior oncology therapies are defined as any anti-cancer therapy stopped before 3 weeks prior to initiation of study treatment.

Prior oncology therapies include prior oncology chemotherapy and oncology medication, prior oncology radiotherapies and prior oncology surgeries/procedures.

Prior oncology medications will be coded using World Health Organisation Drug Dictionary Enhanced (WHO-DDE) version SEPT 2024. Medications will be presented by Anatomical Therapeutic Chemical (ATC) level 2 text and preferred term (PT). ATC class and PT will be sorted in descending frequency of the total number of patients with at least one condition in the corresponding category, ATCs/PTs will be presented alphabetically for ATCs/PTs of the same total frequency.

Prior oncology surgeries/procedures will be coded using Medical Dictionary for Regulatory Activities (MedDRA) Version 27.1 and presented with system organ class (SOC) and PT in a listing.

Radiotherapies are not considered a line of prior oncology therapy. Radiotherapies will be listed in the listing of prior therapies.

Prior oncology medication therapies will be summarized with the following items:

- Number and percentage of patients with at least one prior oncology medication therapy
- Number and percentage of patients with 1, 2, 3, and >3 previous lines of therapy
- Number of max regimens of prior oncology medication therapy
- Time since last oncology medication therapy (month) = (date of first dose – last date for the last therapy + 1) / 30.4375
- Best response for last oncology medication therapy

## 13. MEDICAL HISTORY

Medical History information will be presented for the FAS.

HMPL-523

All medical history from eCRF page ‘Medical History’ will be coded with MedDRA Version 27.1 and summarized by SOC and PT. Number and percentage of patients will be presented in frequency tables, ordered by primary SOC and PT in descending order of the frequency in total group. For SOCs or PTs with the same frequency, categories will be sorted alphabetically.

## 14. CONCOMITANT MEDICATIONS AND PROCEDURES

### 14.1. PRIOR AND CONCOMITANT MEDICATIONS

Medications will be presented for the FAS and will be coded using WHO-DDE version SEPT 2024.

Refer to [Section 7.9](#) for handling of missing or partial dates. In the case where it is not possible to define a medication as prior or concomitant based on dates, the medication will be classified as concomitant.

‘Prior’ medications are medications which started and stopped prior to the day of the first administration.

‘Concomitant’ medications are those which:

- Started prior to the first administration date of study medication and ended on or after the first administration date on treatment.
- Started on or after the first administration date of study medication but no later than 37 days following last administration date on treatment or start of a new treatment of anti-neoplasm therapy, whichever is earlier.

Prior and concomitant medications will be presented by ATC level 2 text and PT. ATC class and PT will be sorted in descending frequency of the total number of patients with at least one condition in the corresponding category, ATCs/PTs will be presented alphabetically for ATCs/PTs of the same total frequency.

### 14.2. CONCOMITANT PROCEDURES

Concomitant procedures are defined as procedures that occurred at any time on or after the day of the first administration and no later than 37 days following the last administration date on treatment of study medication or start of a new treatment of anti-neoplasm therapy, whichever is earlier. Procedures will be presented for the FAS and will be coded using MedDRA Version 27.1 or higher. Concomitant procedures will be summarized and listed by SOC and PT. Number of patients and percentage in the analysis set will be presented in frequency tables, ordered by

HMPL-523

primary SOC and PT in descending order of the frequency in total group. For SOC's or PT's with the same frequency, categories will be sorted alphabetically.

### 14.3. SUBSEQUENT MEDICATIONS AND NON-DRUG TREATMENTS

Subsequent oncology therapy is defined as any new anti-neoplastic therapy (including medication, surgery/procedure, and radiotherapy) started after last dose of study medication. Subsequent oncology therapy will be summarized and listed for the FAS.

## 15. STUDY MEDICATION EXPOSURE AND COMPLIANCE

Exposure to study medication in days will be summarized based on the FAS.

The date of first study medication administration will be taken from the "HMPL-523 Treatment" eCRF form. The date of last study medication will be taken from the last study medication administration date.

Study drug interruptions, compliance, and dose changes are not taken into account for duration of exposure.

The following study medication administration summaries will be reported for this study:

- Number of cycles: the number of cycles in which the patient took any dose of study medication.
- Total duration exposure (months):

$$\text{Total duration of treatment (months)} = \left( \frac{\text{date of last dose} - \text{date of first dose} + 1}{30.4375} \right)$$

It will be summarized as continuous variables and also categorized into groups as below:

- < 6 months exposure
  - $\geq 6$  to < 12 months exposure
  - $\geq 12$  months exposure
- Actual duration of study treatment (months):

Actual duration of study treatment is defined as the total number of months on the study medication during the treatment phase (excluding the periods of dose discontinuation or dose interruptions).

- Cumulative dose (mg):

Cumulative dose (mg) is defined as the sum of the total doses patient actually received during an exposure period.

HMPL-523

- Dose intensity (mg/day):

$$\text{Dose intensity (mg/day)} = \left( \frac{\text{Cumulative dose (mg)}}{\text{total treatment exposure(days)}} \right)$$

- Relative dose intensity (%):

$$\text{Relative dose intensity (\%)} = \left( \frac{\text{dose intensity (mg/day)}}{\text{planned dose intensity(mg/day)}} \right) * 100$$

The planned dose intensity is defined in the protocol for each cohort: 100mg/day, 200mg/day, 400 mg/day, 600 mg/day, 700 mg/day, and 800 mg/day.

It will be summarized as continuous variables and also categorized into groups as below:

- < 50%
- 50% - <70%
- 70% - <90%
- 90% - <110%
- $\geq$ 110%

The number and percentage of patients with any dose modification will be presented. Dose modification will be further characterized by presenting the numbers and percentages of patients with any dose reduction, dose escalation and dose interruption. Reasons for dose adjustments will be summarized as well.

Details of study treatment administration will be included in patient listings.

## 16. EFFICACY OUTCOMES

Tumor assessment will be conducted every 8 weeks ( $\pm$  7 days) for the first 24 weeks and then every 12 weeks ( $\pm$  7 days) thereafter.

Efficacy analysis will be performed using the RES for ORR, TTR, and DoR endpoints and using the FAS for the PFS endpoint.

Unless otherwise specified, all efficacy outputs are to be summarized by dose cohort for Stage 1 and by type of malignancy in Stage 2.

HMPL-523

## 16.1. EFFICACY PARAMETERS

### 16.1.1. EFFICACY PARAMETERS & DERIVATIONS

Efficacy in different malignancies will be evaluated according to specified guidelines/criteria:

- CLL: modified IWCLL 2008
- WM/LPL: IWWM-7

#### Best overall response (BOR)

The best overall response (BOR) for an individual patient is the best response recorded from the start of treatment until progression or the date of any further anticancer therapy, whichever comes first.

Best overall response is determined from the sequence of responses assessed as below:

- For CLL guideline: Complete Response (CR), CR with incomplete bone marrow recovery (CRi), Partial Response (PR), Nodular Partial Response (nPR), Partial Response with Lymphocytosis (PR-L), Stable Disease (SD), Progressive Disease (PD), Not all evaluated (NE).
- For WM guideline: Complete Response (CR), Very Good Partial Response (VGPR), Partial Response (PR), Minor Response (MR), Stable Disease (SD), Progressive Disease (PD), Not Evaluated (NE).
- For Other Lymphomas guideline: Complete Response (CR), Partial Response (PR), Stable Disease (SD), Progressive Disease (PD), Not Evaluated (NE).

For patients with multiple assessment for same visit, the earliest date will be selected for PD, while the latest date will be selected for other response.

Patients with BOR "NE" will be summarized by reason for having NE status. The following reasons will be used:

- No valid post-baseline assessment
- All post-baseline assessments have overall response NE

Patients with a BOR of "Unknown" or "NE" will be considered non-responders in estimating response rates.

HMPL-523

The number and percentage of patients with BOR of CR, CRi, VGPR, PR, nPR, MR, PR-L, SD, PD, and NE will be summarized by dose level and overall in Stage 1, by the malignancy type and overall in Stage 2.

### **Objective response rate (ORR)**

ORR is defined as the proportion of patients who have BOR with CR, CRi, nPR or PR for CLL patients; the proportion of patients who have BOR with CR, VGPR, PR or MR for WM patients; the proportion of patients who have BOR with CR or PR for patients with disease type other than CLL and WM.

The definition of neo-OR is similar with that of classical OR except that partial response with lymphocytosis (PR-L) is also included for CLL.

The estimated ORR and 95% Clopper-Pearson CI (Clopper, C. J., & Pearson, E. S. 1934) will be presented by dose level for Stage 1 and by the malignancy type for Stage 1 and Stage 2.

### **Complete Response Rate (CR rate)**

CR rate is defined as the proportion of patients who have BOR with CR or CRi for CLL patients, and CR only for other patients.

The estimated CR rate and 95% Clopper-Pearson confidence interval (CI) (Clopper, C. J., & Pearson, E. S. 1934) will be presented by dose level for Stage 1 and by the malignancy type for Stage 2.

### **Clinical Benefit Rate (CBR)**

CBR is defined as the proportion of patients who have BOR of stable disease (SD) or better.

The clinical benefit for each type of malignancy is defined as following:

- CLL: BOR with CR, CRi, nPR, PR, PR-L or SD
- WM: BOR, with CR, VGPR, PR or SD, MR
- Other types of disease: CR, PR or SD

The estimated CBR and the corresponding 95% exact CI using Clopper-Pearson method (Clopper, C. J., & Pearson, E. S. 1934) will be summarized for presented by dose level in Stage 1 and type of the malignancy for Stage 2.

CBR data will be listed for all patients in RES.

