5.6.12 Tumor and Response Evaluation

All evaluable lesions should be assessed and documented at screening and re-assessed at each subsequent tumor evaluation, using blood test, physical examination, and contrast-enhanced CT scans (neck, chest, abdomen, and pelvis) for indolent NHL and/or positron emission tomography (PET)-CT for HL and aggressive NHL. Enhanced magnetic resonance imaging (MRI) may be used instead of enhanced CT scans in patients for whom CT scans are contraindicated.

Tumor assessment will be conducted every 8 weeks (± 7 days) for the first 24 weeks and every 12 weeks (± 7 days) thereafter until the patient has the first progression, starts new anticancer therapy, or dies. Patients who discontinue study drug due to reasons other than disease progression will remain on the study and will be followed quarterly for tumor assessment until the patient has their first progression, starts new anticancer therapy, or dies or until 12 months after their initial dose of the study drug. Tumor assessment will also be conducted at study completion or early termination (for reasons other than disease progression).

The same imaging procedure and laboratory tests used to define evaluable lesions at baseline should be used throughout the study for each patient.

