**Error! Reference source not found.: Visit Window**

	Cycle 1			Cycle 2		Cycle 3 and onwards	Last Cycle	Follow-up		
	D1	D8 (±1)	D15 (±1)	D22 (±1)	D1 (±3)	D15 (±3)	D1 (±3)	CXD1	Study Completion or Early Termination (30±7 Days After the End of Treatment)	Follow-up on Day 1 (±7) Quarterly After the End of Treatment
Scheduled Day [a]	1	8	15	22	1	15	1	1		
ECOG performance status	Day1		2 to EOC-3		Day -3 to 8	9 to EOC-3	Day -3 to EOC-3	Day-3 to EOC	Last dose date of last cycle +1 to last dose date of last cycle +37	
Vital signs	Day1	2 to 11	12 to 18	19 to EOC-3	Day -3 to 8	9 to EOC-3	Day -3 to EOC-3	Day-3 to EOC		

HUTCHMED Ltd.

CONFIDENTIAL

HMPL-523

									Follow-up	
	Cycle 1				Cycle 2		Cycle 3 and onwards	Last Cycle		
	D1	D8 (±1)	D15 (±1)	D22 (±1)	D1 (±3)	D15 (±3)	D1 (±3)	CXD1	Study Completion or Early Termination (30±7 Days After the End of Treatment)	Follow-up on Day 1 (±7) Quarterly After the End of Treatment
Hematology		1 to 11	12 to 18	19 to EOC-3	Day -3 to 8	9 to EOC-3	Day -3 to EOC-3	Day-3 to EOC		
Urinalysis/ dipstick			1 to EOC-3		Day -3 to 8	9 to EOC-3	Day -3 to EOC-3	Day-3 to EOC		
Chemistry panel		1 to 11	12 to 18	19 to EOC-3	Day -3 to 8	9 to EOC-3	Day -3 to EOC-3	Day-3 to EOC		
Beta 2-microglobulin					Cycle 1 Day 1 to EOC-3		Day -3 to EOC-3	Day-3 to EOC		
Fasting lipid profile					Cycle 1 Day 1 to EOC-3		Day -3 to EOC-3	Day-3 to EOC		
Serum amylase and lipase		1 to 11	12 to 18	19 to EOC-3	Day -3 to 8	9 to EOC-3	Day -3 to EOC-3	Day-3 to EOC		
Coagulation assay (INR, aPTT, PT)					Cycle 1 Day 1 to EOC-3		Day -3 to EOC-3	Day-3 to EOC		
Leukocyte immunophenotyping			1 to EOC-3		Day -3 to EOC-3		Day -3 to EOC-3	Day-3 to EOC		
Echocardiogram/MUGA										

HUTCHMED Ltd.

CONFIDENTIAL

HMPL-523

								Last Cycle	Follow-up	
	Cycle 1				Cycle 2		Cycle 3 and onwards			
	D1	D8 (±1)	D15 (±1)	D22 (±1)	D1 (±3)	D15 (±3)	D1 (±3)		CXD1	Study Completion or Early Termination (30±7 Days After the End of Treatment)
12-Lead ECG	Day 1-2		3 to EOC -3		Day -3 to EOC -3		Day -3 to EOC -3	Day -3 to EOC		
Quantitative serum immunoglobulin levels (for WM/LPL)					Cycle 1 Day 1 to EOC -3		Day -3 to EOC -3	Day -3 to EOC		X
CT/PET-CT							Cycle 1 Day 1 to EOC -3	Day -3 to EOC		X

[a] The scheduled day is relative to Day 1 of each cycle.

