#### **Stable Disease (SD)**

Patients who have not achieved a CR or a PR, or who have not exhibited PD, will be considered to have stable disease

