No response or stable disease	No metabolic response	Stable disease
Target nodes/nodal masses, extranodal lesions	Score 4 or 5 with no significant change in FDG uptake from baseline at interim or end of treatment	< 50% decrease from baseline in SPD of up to 6 dominant, measurable nodes and extranodal sites; no criteria for progressive disease are met
Nonmeasured lesions	Not applicable	No increase consistent with progression
Organ enlargement	Not applicable	No increase consistent with progression
New lesions	None	None
Bone marrow	No change from baseline	Not applicable
Progressive disease	Progressive metabolic disease	Progressive disease requires at least 1 of the following
Individual target nodes/nodal masses	Score 4 or 5 with an increase in intensity of uptake from baseline and/or	PPD progression:

HMPL-523

Response and Site	PET-CT-Based Response	CT-Based Response
Extranodal lesions	New FDG-avid foci consistent with lymphoma at interim or end-of-treatment assessment	An individual node/lesion must be abnormal with: LDi > 1.5 cm and Increase by $\geq$ 50% from PPD nadir and An increase in LDi or SDi from nadir 0.5 cm for lesions $\leq$ 2 cm 1.0 cm for lesions > 2 cm In the setting of splenomegaly, the splenic length must increase by > 50% of the extent of its prior increase beyond baseline (eg, a 15-cm spleen must increase to > 16 cm). If no prior splenomegaly, must increase by at least 2 cm from baseline New or recurrent splenomegaly
Nonmeasured lesions	None	New or clear progression of preexisting nonmeasured lesions
New lesions	New FDG-avid foci consistent with lymphoma rather than another etiology (eg, infection, inflammation). If uncertain regarding etiology of new lesions, biopsy or interval scan may be considered	Regrowth of previously resolved lesions A new node > 1.5 cm in any axis A new extranodal site > 1.0 cm in any axis; if < 1.0 cm in any axis, its presence must be unequivocal and must be attributable to lymphoma Assessable disease of any size unequivocally attributable to lymphoma
Bone marrow	New or recurrent FDG-avid foci	New or recurrent involvement

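### SAP 16.1.1 sets no minimum time from first dose for stable disease, so a single early SD scan counts as clinical benefit

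*SAP*

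**What the plan says.** SAP 16.1.1 defines the measure: "CBR is defined as the proportion of patients who have BOR of stable disease (SD) or better". It is to be estimated with an exact 95% interval, by dose level in Stage 1 and by malignancy in Stage 2. The same section takes BOR as "the best response recorded from the start of treatment until progression or the date of any further anticancer therapy, whichever comes first".

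The SD definitions contain no duration. For CLL, SAP Appendix 4 makes SD the residual category: "Patients who have not achieved a CR or a PR, or who have not exhibited PD, will be considered to have stable disease". For lymphomas under Lugano, the CT-based definition in Appendix 6 asks for less than a 50% decrease and that "no criteria for progressive disease are met". The Waldenström table in Appendix 5 also gives SD no time requirement.

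On timing, SAP section 16 states: "Tumor assessment will be conducted every 8 weeks", with a 7-day window either side, for the first 24 weeks. Protocol 5.6.12 adds an off-schedule scan: "Tumor assessment will also be conducted at study completion or early termination (for reasons other than disease progression". Protocol 5.7.1 and the Schedule of Activities place that visit 30 ± 7 days after the last dose.

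CBR is not in the protocol's list of efficacy measures (4.8.4), which names ORR, DoR, TTR and PFS.

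**The concern.** Because BOR keeps the best reading before progression, a patient with one SD scan and progression at the next still has BOR of SD and counts as benefiting. Nothing requires the qualifying scan to be the Week 8 scan or later.

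This has two consequences. First, in a single-arm study a single unchanged scan at Week 8 partly measures how fast the disease moves without treatment, and the name of the measure invites a reader to credit the drug. Second, a patient who stops for toxicity in the first weeks can qualify on a scan taken well before Week 8, when fewer patients have had time to progress. That bias runs in one direction: the earlier the scan, the more likely it reads SD. By contrast, Appendix 4 asks for PR features in CLL to hold for at least 2 months, but attaches no time to SD.

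**Working it through.** The documents give no CBR rate, reference rate or threshold, so there is no plan figure to reproduce.

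**1. Earliest early-termination scan.** Let the last dose fall on study day L. The visit falls between study days L + 23 and L + 37.
- L = 1 (a single dose): days 24 to 38.
- L = 12: days 35 to 49.
- L = 20: days 43 to 57.
- L = 26: days 49 to 63.

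Week 8 is 56 days after first dose, which is study day 57. The early edge of its window is study day 57 − 7 = 50. An early-termination scan can precede day 50 only if the patient stops by study day 26, and must do so if the patient stops by study day 12. Unscheduled assessments (Protocol 5.6.1) could also fall early.

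**2. Share qualifying with an inactive drug.** Assume exponential time to progression with median m months. Neither the form nor the medians are in the documents. With 30.4375 days per month, the share free of progression d days after first dose is 0.5^(d / 30.4375 / m).

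| Scan | d | m = 1 | 1.5 | 2 | 3 | 6 |
|---|---|---|---|---|---|---|
| Study day 24 | 23 | 59% | 71% | 77% | 84% | 92% |
| Study day 50 (Week 7) | 49 | 33% | 48% | 57% | 69% | 83% |
| Week 8 | 56 | 28% | 43% | 53% | 65% | 81% |
| Week 24 | 168 | 2% | 8% | 15% | 28% | 53% |

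Example: d = 56 is 56 / 30.4375 = 1.84 months. For m = 2 the share is 0.5^(1.84 / 2) = 0.529.

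**3. Break-even.** The share is one half when m equals the scan time in months: 1.84 at Week 8 (1.61 at Week 7, 2.07 at Week 9) and 5.52 at Week 24.

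**4. Illustration for the Stage 2 mix.** Protocol Table 2 gives HL 25, PTCL 9, CLL 1 + 7 (post-BTK), FL 2, MCL 2, MZL 1, WM/LPL 1 and CBCL 0, total 48. With assumed no-drug medians for HL, PTCL, MCL and CLL/indolent disease respectively, the pooled Week 8 share is:
- 1.5, 1, 1.5 and 4 months: 47.5%
- 2.5, 1.5, 2 and 6 months: 61.7%
- 4, 2, 3 and 12 months: 73.0%

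The result falls on either side of one half, depending on assumptions the documents cannot settle.

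**The case against.** The strongest reply is that little depends on CBR. It has no reference rate, test or threshold, and the protocol's efficacy measures are unaffected. The SAP already reports SD, PD and NE separately in the BOR table, and plans PFS rates at 6 and 12 months. That stands, and it limits the severity. It does not close the gap, because the BOR table shows how many patients have SD but not when it was read.

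Patients who stop for reasons other than progression also stay under quarterly scanning (Protocol 5.6.12). That is true, but a later PD does not displace an earlier SD under the BOR rule.

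Several stronger readings are tempting and are not supported:
- *Most patients would count even if the drug did nothing.* This needs a no-drug median above about 1.84 months, which the documents do not give. The shortest median PFS they report is 1.9 months, on drug, in the DLBCL/FL Grade 3b cohort of the Chinese study (Protocol 2.2.4.4), so shorter untreated medians cannot be set aside.
- *Slow-growing disease makes a high rate inevitable.* CLL, FL, MZL and WM/LPL account for 8 + 2 + 1 + 1 = 12 of 48 expansion patients; HL and PTCL account for 34. Results are shown by malignancy.
- *An early-termination scan at Day 20 can qualify.* The visit rule puts the earliest such scan at study day 24.
- *SD at any time counts.* It must precede progression and new therapy.
- *SD must last to Week 24.* This is a choice, not a correction. At a 6-month median the no-drug share is still 53%, and the planned 6-month PFS rate covers much the same ground.

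**Conclusion.** The gap is real and is visible from the text alone: no rule in SAP 16.1.1 or its response appendices sets a minimum time for SD, and a qualifying reading can precede the first planned scan by about a month (study day 24 against day 57). A substantial share of patients, possibly a majority, could qualify at Week 8 without any drug effect: 28% to 81% across assumed exponential medians of 1 to 6 months. Whether it exceeds one half in this trial is not shown. The early-scan bias affects mainly patients who stop within about the first 26 days; the documents do not say how many did. Since CBR is descriptive and no decision follows from it, this is a definition and labelling point of limited impact.

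**What to change.** In the CBR derivation in SAP 16.1.1:
- Count SD only if it is documented on or after study day 50. A patient whose only evaluable reading is an earlier SD stays in the denominator and is not counted as benefiting.
- Leave the recorded BOR categories and every response category unchanged.
- Label the measure disease control (SD or better at Week 8 or later, allowing the 7-day window), and show it beside the planned 6-month PFS rate.
- Name the denominator in the same edit. SAP 6.2 assigns efficacy other than ORR, TTR and DoR to the FAS, while the CBR paragraph lists CBR for the RES.

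The cost is SAP wording and one date condition, finalized before database lock. No new data are needed. The reported rate may fall slightly. The day-50 rule removes the advantage of very early scans; it does not remove the background rate at Week 8, which is why the label and the PFS rate beside it matter. Requiring SD to Week 24 may be added as an optional alternative.
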